Analytic Plan AIM 2: To test **H2**, we will use the network information from Aim 1 to analyze correlation of knowledge, attitudes, and behaviors between members of the network (transplant discussions, living donor recruitment, and step in kidney transplant process) from the surveys and the EMR.

Primary Outcome: Correlation of 1) attitudes about transplantation and 2) step in transplant process

Independent Variables: Clustering coefficient and attributes of alters

Covariates: Age, Marital Status, HD vintage, insurance, transplant eligibility, HD clinic, network attributes

Analysis: We will examine how knowledge, attitudes, and completion of steps differ by network attributes. These differences will then be validated by using logistic regression modeling to predict patient's attitudes towards transplantation and step in the transplant work-up using demographic and survey variables. We will then add network attributes and quantify the improvement in the prediction model using tests for goodness of fit. To further validate the model we will perform an Exponential Random Graph Model (ERGM) with temporal attributes⁵³ in which the patients current transplant step is a function of patients baseline data and network attribute as well as their alters' baseline step, current step, and network attributes.

Limitations: We have previously found that patients are often incorrect about their listing status⁴, thus we will confirm the transplant status by contacting the listing institution. Using the steps completed will allow for the analysis of patients that are highly motivated who complete all their work-up but are discovered to have an absolute contraindication to transplantation. Since AIM 1 and 2 are observational, we will be unable to determine whether patients form small networks with like-minded individuals or whether over time everyone in a small network will reach a common belief through spread of information and behaviors⁵⁴. To test the spread of information and behaviors, in **AIM 3**, we will use a network targeted intervention.

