AIM3: Compare and contrast the diffusion of knowledge, attitudes, and behaviors regarding transplantation through HD social networks by targeting either the most central or the most clustered members of the network to disseminate a transplant education intervention. **H3:** Targeting patients with high clustering coefficients will be the most effective method for the spread of knowledge and favorable attitudes toward transplantation, and completing steps toward transplantation as compared to targeting by centrality.

Rationale: Previous studies have shown that barriers to transplantation tend to be less about information but rather behaviors related to completing the transplant steps^{1,2,4,13}, thus dense social networks are likely to be more effective in changing behavior and participating in a social network than diffuse networks, which are more effective at spreading novel information³²⁻³⁴.

Patient Recruitment, Eligibility, and Retention AIM 3: One year after the initial survey, we will use a targeted network intervention to measure the spread of information, attitudes, and behaviors. We will target transplant eligible patients based on their clustering coefficient or their betweenness centrality to participate in the COACH education using data collected in AIMS 1 and 2.

Recruitment Goals: Based on previous research^{1,4}, we anticipate approximately half the patients would be eligible for a kidney transplant but not on the list. If 250 patients participate in **AIM 1 and 2**, then at least 125, or approximately 10 patients per shift will be eligible for the intervention. The intervention will target either the two most central transplant eligible patients or the two most clustered patients to participate in the COACH education. As this is a social network intervention, although we are targeting only two patients per shift, all the patients on that shift are considered exposed to the COACH education. To prevent selecting a patient that is both relatively central and clustered, the patients selected by centrality will have a centrality greater than 1 standard deviation (SD) from the mean and a clustering less than 1 SD from the mean. Conversely, the

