Exposure: While only two patients per shift will receive the COACH intervention, all patients regardless of participation in the COACH education will be analyzed as exposed to the intervention via social spread. This will result in two groups for the primary analysis Cluster (MWF1 Cluster + TTS2 Cluster) and Central (MWF2 Central + TTS1 Central)

Analysis: To measure global changes, we will use a t-test to test changes in knowledge and changes in completion of steps between Cluster and Central. Individual level transfer of information will be analyzed with a

Markov chain Monte Carlo accept-reject procedure in the chain⁵⁸. We will examine the correlation in changes of a patient's(ego) knowledge with his or her first degree alter and measure the decay in correlation as the degree of the alter increases. We will also examine the ego's distance (how many links the patients are from each other) from the alter receiving the intervention. In addition, we will use Gaussian Conditional Random Fields (GCRF) methods to model a patient's stage in the transplant process by taking into account various factors such as personal demographics, social influence of alters, and global trends of HD shift and clinic⁵⁹. We will examine the characteristics of the patients disseminate and receive information. The data directly measuring the spread of information, influence, and behavior within the network from this experiment will be used to validate and strengthen the social network model developed in AIM1 and AIM2.

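### The Aim 3 ego-alter correlation of knowledge changes cannot by itself show spread; claims should rest on distance from the COACH recipient, set against the COACH-free first year

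*SAP*

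**What the plan says.** Under Aim 2, Limitations, the SAP concedes that observational network data cannot show "whether patients form small networks with like-minded individuals or whether over time everyone in a small network will reach a common belief". The remedy is the next aim: "To test the spread of information and behaviors, in" Aim 3, a network-targeted intervention will be used.

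The Aim 3 Analysis paragraph then lists several individual-level analyses. One will correlate changes in a patient's "knowledge with his or her first degree alter and measure the decay in correlation as the degree of the alter increases". That sentence names no COACH receipt, no assignment and no survey wave. The sentence after it does bring COACH in: "We will also examine the ego's distance (how many links the patients are from each other) from the alter receiving the intervention". Staggered Surveys and the Aim 3 Limitations add a question on where new knowledge came from. The paragraph ends by using the experiment's data to validate the Aim 1 and 2 model: "The data directly measuring the spread of information, influence, and behavior within the network from this experiment".

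On timing, the SAP says: "One year after the initial survey, we will use a targeted network intervention to measure the spread of information, attitudes, and behaviors". The Timeline puts Wave 1 in Year 2 Q1, Wave 2 in Year 3 Q1, Wave 3 in Year 3 Q2 and Wave 4 in Year 4 Q1. Staggered Surveys places a survey of targeted patients before COACH and surveys non-recipients alongside them; Participant Remuneration covers all patients at Wave 2. Recipients are two transplant-eligible patients per shift, picked for high betweenness centrality or high clustering.

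**The concern.** Aim 3 is there to settle what Aims 1 and 2 cannot: whether linked patients are alike because they chose each other or because something passed between them. A correlation of changes over all linked pairs, whether or not either patient is near a COACH recipient, does not use the intervention that was meant to settle it. If patients with similar motivation sit together and learn at similar rates, their changes correlate most at one link and less at two, with nothing transmitted. At stake is that a decaying correlation could be read as evidence of spread and carried into the network model. Wave 1 to Wave 2 offers a year of change without COACH, and nothing in either document runs this correlation, or the distance analysis, on that year as a comparison.

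**Working it through.** **The plan's own figures.** The SAP gives no power, target or test for the ego-alter correlation. Its nearest figures are for the Cluster-versus-Central t-tests, and they reproduce (two-sided, alpha 0.05): effect size 1.06 with 15 per arm gives power 0.800; 0.6 (half of 1.2) with 45 per arm gives 0.804. They do not bear on this point.

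**Inputs from the SAP.** 252 expected participants; 2 clinics x 6 shifts = 12 shifts; 252 / 12 = 21 per shift; 2 x 12 = 24 recipients; 252 - 24 = 228 non-recipients before dropout.

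**Inputs assumed.** About 2.8 ties per patient, ties likelier between patients alike on a latent trait u, and the size of all effects. The documents give no tie density, homophily strength or SD of knowledge change.

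**Why level cancels and rate does not.** If a score is a stable level plus noise, the level drops out of the change. If instead change = r·u + noise, the correlation of changes at k links is approximately v x rho_k, where v is the share of the variance in change due to u and rho_k is the correlation of u at k links. With r = 0.9 and noise SD 1.2, v = 0.81 / (0.81 + 1.44) = 0.36. The simulated one-link correlation before COACH was 0.166, so rho_1 is about 0.166 / 0.36 = 0.46.

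**Simulation 1** (400 runs; COACH adds 2.5 points to each recipient; recipients drawn at random among linked patients). Correlation of changes at 1 / 2 / 3 links, and slope of change on links to the nearest recipient:

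| Setting | Correlation before COACH | Correlation after COACH | One-link, after minus before (SD) | Slope before / after |
|---|---|---|---|---|
| Shared rate, no spread | 0.17 / 0.07 / -0.01 | 0.11 / 0.04 / -0.02 | -0.06 (0.08) | 0.00 / -0.01 |
| Shared level only, no spread | 0.00 / 0.00 / -0.01 | -0.02 / -0.02 / -0.02 | -0.02 (0.07) | 0.00 / 0.00 |
| COACH spread, no shared rate | -0.01 / 0.00 / -0.01 | 0.10 / 0.01 / -0.05 | +0.10 (0.08) | 0.01 / -0.46 |
| Shared rate and COACH spread | 0.16 / 0.07 / -0.01 | 0.17 / 0.05 / -0.04 | +0.01 (0.08) | 0.01 / -0.44 |
| Ordinary peer spread in both periods | 0.28 / 0.05 / 0.00 | 0.25 / 0.02 / -0.03 | -0.03 (0.09) | -0.01 / -0.16 |

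After COACH, the first and third rows are nearly the same pattern. The difference between correlations does not rescue the analysis: at best it is 0.10 / 0.08 = 1.25 SD, and it is near zero when both mechanisms operate. One reason is that a recipient's own gain, not matched by the neighbours, lowers the correlation.

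**Range.** Two further sets of runs, with ties formed in proportion to exp(-h|u_i - u_j|), agree. With no COACH effect, no spread and 20-40% of the variance in change shared, the one-link correlation was 0.07 to 0.18, or 0.04 to 0.08 with weaker homophily. At h = 1 and 30% shared, it was 0.11 / 0.02 / -0.03.

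**Simulation 2** (500 runs; recipients are the two most connected patients per shift, a stand-in for most central; slope among non-recipients, points per link):

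| Setting | Wave 1-2 | After COACH | Difference (SD) |
|---|---|---|---|
| No spread, connected patients improve faster | -0.18 | -0.17 | 0.00 (0.14) |
| COACH spread, connected patients improve faster | -0.16 | -0.59 | -0.42 (0.15) |

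The post-COACH slope alone misleads in the first row; the difference does not. With spread it is 0.42 / 0.15 = 2.8 SD. A separate set of runs gave -0.22 (SD 0.08) with spread against about 0 without.

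**The case against.** **The plan has other evidence on spread.** A reader might infer that Aim 3's individual-level work as a whole ignores COACH. It does not: the distance analysis is anchored on the recipient, and patients are asked where new knowledge came from. Nor does the closing sentence about measuring spread belong to the correlation alone; it describes the data from the whole experiment. The SAP nowhere says that a decaying correlation by itself will count as spread. All of this stands, and it narrows the point to one analysis plus an adjustment to a second.

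**Changes remove like-mindedness.** This is true for similarity in level, as the second row of the first table shows. The pattern needs a shared rate of change, or shared influences, and the documents do not show that this holds here. On a bounded 12-item score with response noise, the shared-rate correlation fell to 0.03 before and 0.01 after COACH. No matching run with spread was made on that scale, so the side-by-side comparison is for a continuous score.

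**The first year is used.** Change from baseline is assessed before COACH, and the Aim 2 random graph model uses alters' baseline and current steps. The year is unused only as a comparison for these two analyses.

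**The first year is not free of spread.** Ordinary conversation between patients can pass on knowledge in Wave 1-2 as well. A reader might infer that the comparison separates spread from like-mindedness in general. It does not; it isolates what COACH added.

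**Learning from repeated surveys may differ between intervals.** An effect common to all patients moves the mean change, not its slope on distance, so this matters only if it varies with distance.

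**The cited Markov chain Monte Carlo procedure may supply a null.** The SAP does not say what it conditions on, so this cannot be judged from the documents.

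**Conclusion.** The point holds in a limited form. The ego-alter correlation and its decay cannot distinguish COACH spread from linked patients who share a rate of change, so for this analysis the ambiguity admitted under Aim 2 remains. Under the assumed inputs, the spurious one-link correlation is about 0.04 to 0.18 on a continuous score and close to zero on a noisy bounded one. That it can arise is shown; how large it would be here is not known.

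The distance-from-recipient analysis is the better basis, but selection by network position can give it a slope without spread. This applies under either document: the SAP takes two patients per shift, the protocol (Study Procedure and Data Analysis, item iv) one chosen at random on a network attribute. That conflict needs reconciling.

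A reader might go on to doubt the primary result. The documents do not support that: H3 is tested by comparing Cluster with Central shifts, and nothing here touches that comparison. The matter deserves correction because it affects how spread is interpreted.

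**What to change.** 1. Label the ego-alter correlation and its decay by degree descriptive. Report the same correlation for Wave 1-2 change beside Wave 2-4 change as a negative control, and base no claim on the difference between the two.
2. Name the distance-from-recipient analysis, among non-recipients, as the basis for any claim of COACH-related spread. The estimate is the slope of Wave 2-4 knowledge change on distance minus the slope of Wave 1-2 change on the same distances, with intervals that resample shifts.
3. Take the distances from one network map fixed before COACH, state how patients with no path to a recipient are handled, and confirm that non-recipients complete Wave 2 before COACH starts on their shift.
4. State that the contrast isolates COACH-related spread only.

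Both intervals are about 12 months. They also correspond to the protocol's baseline and two annual surveys, so the contrast does not depend on the 3-month wave, which the protocol describes inconsistently (for COACH patients only in one place, for all patients in another).

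The cost is a few reruns on data already planned. The contrast is less precise than a single slope, and resampling 12 shifts gives rough intervals. Precision may be lower than simulated: in the sponsor's previous study 67% of patients were linked, and at that rate about 228 x 0.67 = 153 non-recipients would be linked at all, before dropout.

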Limitations: If the targeted patient refuses to participate, we will select another two transplant eligible patients to participate in the intervention based on their clustering and centrality. The network attributes of the patients if they refuse to participate will be analyzed and can inform AIMS 1 and 2 as well as recruitment strategies for future studies. In the unlikely event no patients on the shift participate in the COACH education, they will be analyzed as intention to treat. Since we are measuring change in knowledge using repeated surveys we are at risk for a learning effect⁶⁰. For this reason on the repeated survey questionnaires, we will also assess where the new knowledge came from patient interactions or self-reading after the survey. Given the focus of the proposed research on urban and suburban locales, future research is indicated to see if this social network mapping and intervention can also be used in rural settings, especially since recent studies shown many patients in rural southeast are disadvantaged regarding transplantation⁶¹.

Sample size and power AIM3: Using the data from our previous HD clinic social network study, we expect the patients in the Clustering targeted intervention to complete at least 2 more steps in the transplant work-up than those in the Centrality intervention (7, SD 1.5 vs 5, SD 1.7, p=0.03). The observed effect size was 1.06 or a difference of 2 steps. We estimate at least 10 patients per shift will be exposed to the intervention either directly through participation in the intervention or indirectly through information/behavior spread through the social network. Both clinics have 6 shifts, and we would have 60 patients assigned to each intervention condition. Based on a two tailed t-test, a total sample of 30 (15 in each treatment arm) would yield 80% power at significance level $\alpha = 0.05$ to detect a difference of 2 steps. With 120 patients (60 patients in each treatment arm) we will be powered to detect a difference of 1 step. The COACH intervention produced a change in knowledge³ with an effect size of 1.2, thus if we expose 90 patients (45 in each arm) to the intervention, we will have the power to detect at least half that effect.

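### The steps effect size of 1.06 does not follow from the printed means and SDs (they give 1.25), and the knowledge power is benchmarked on COACH's own effect although both arms deliver COACH

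*SAP*

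**What the plan says.** **Steps** (SAP, Sample size and power AIM3). From the team's earlier dialysis-clinic network study, the SAP expects patients in the Clustering arm to "complete at least 2 more steps in the transplant work-up than those in the Centrality intervention". The supporting data are "7, SD 1.5 vs 5, SD 1.7, p=0.03). The observed effect size was 1.06 or a difference of 2 steps", with no group sizes. It then states that "a total sample of 30 (15 in each treatment arm) would yield 80% power" with a two-sided t-test at 0.05 for a 2-step difference, and that 60 per arm covers 1 step without naming a power.

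**Knowledge** (same paragraph). COACH is reported to have changed knowledge "with an effect size of 1.2, thus if we expose 90 patients (45 in each arm) to the intervention", from which the SAP claims power for at least half that effect.

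**What is compared.** Under Analysis (Aim 3), "we will use a t-test to test changes in knowledge and changes in completion of steps between Cluster and Central". Under Recruitment Goals (Aim 3), "The intervention will target either the two most central transplant eligible patients or the two most clustered patients to participate in the COACH education". Both arms therefore contain COACH-taught patients and differ in how those patients are chosen.

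**Related statements.** In Analytic plan AIM3 the prose places knowledge among the secondary outcomes, while the outcome list just below puts it first under primary outcomes. Protocol 7.d.iv selects one patient per shift for COACH; the SAP's Exposure paragraph says "While only two patients per shift will receive the COACH intervention".

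**The concern.** Two things look wrong, and they differ in kind.

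(a) The means, SDs and effect size sit side by side and do not agree. The SAP calls 1.06 observed and equates it with 2 steps, but no average of the two printed SDs gives that value. A reader cannot tell which figure to carry forward.

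(b) The knowledge benchmark belongs to another contrast. An effect produced by COACH says how much teaching moves knowledge. It does not say how much further knowledge spreads when the taught patients are chosen by clustering rather than centrality, which is what the between-arm t-test addresses. Detecting half of the COACH effect sounds comfortable, but the SAP offers nothing to show whether a between-arm gap of that size is plausible. This matters more if knowledge is a primary outcome, which the SAP leaves unresolved.

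**Working it through.** **Inputs** (SAP, Sample size and power AIM3): means 7 and 5; SDs 1.5 and 1.7; effect size 1.06; two-sided alpha 0.05; 15, 60 and 45 per arm; COACH knowledge effect 1.2. Powers are from the noncentral t distribution with independent patients, as the SAP assumes.

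**1. Reproduce the SAP's own figure.** With d = 1.06 and 15 per arm, power is 80.0%. So N = 30 does follow from 1.06.

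**2. Does 1.06 follow from the printed data?**
- Pooled SD = √[(1.5² + 1.7²)/2] = √2.57 = 1.603.
- d = (7 − 5)/1.603 = 1.25.
- Using one SD only: 2/1.7 = 1.18; 2/1.5 = 1.33. Every weighting of the two lies between these, so none reaches 1.06.
- A small-sample (Hedges) correction reaches 1.06 only with 7 to 9 patients in total, where the pooled-t p-value is at least 0.15, not 0.03.

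**3. Where could 1.06 come from?**
- *A different SD:* 2/1.06 = 1.89, above both printed SDs.
- *Rounded means:* 1.06 × 1.603 = 1.70 steps. For example, 6.8 and 5.1 print as 7 and 5, and (6.8 − 5.1)/1.603 = 1.06.
- *A mislabelled detectable effect:* the smallest effect with 80% power at 15 per arm is 1.0598. Software output may have been labelled as observed. This is an inference.

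The printed p-value does not decide between them without group sizes. With equal groups, d = 1.25 gives p = 0.038 at 7 per group and 0.026 at 8; d = 1.06 gives 0.029 at 10.

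**4. Do the power statements survive?**

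| SD | 2 steps, 15 per arm | 1 step, 60 per arm |
|---|---|---|
| 1.60 (printed) | 91% | 92% |
| 1.89 (implied by 1.06) | 80% | 82% |

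Yes, at both SDs. Allowing for rounding of the SDs (1.45 to 1.75), power for 2 steps at 15 per arm is 95% to 86%.

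**5. Knowledge.** Half of 1.2 is 0.6. With 45 per arm, d = 0.6 has 80.4% power, so the arithmetic reproduces. At 60 per arm, the effect detectable with 80% power is 0.52 SD.

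The SAP states no Cluster-minus-Central knowledge difference. For an assumed range:

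| Assumed difference (SD) | Power, 45 per arm | Power, 60 per arm |
|---|---|---|
| 0.2 | 16% | 19% |
| 0.3 | 29% | 37% |
| 0.4 | 47% | 58% |
| 0.5 | 65% | 78% |

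**6. Where 1.2 could apply.** Staggered Surveys plans a pre-post assessment and a comparison of taught with untaught patients. With 6 shifts in each of 2 clinics, 1 or 2 taught per shift gives 12 or 24 taught. Among 90 patients that is 12 vs 78 or 24 vs 66, not 45 vs 45. Power at 1.2 is 97% or 99.9%; at 0.6 it is 48% or 70%.

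**The case against.** The strongest reply on (a) is rounding. The means are printed in whole steps. An unrounded difference of 1.70 gives d = 1.06, p = 0.029 at 10 per group, and 80% power at 15 per arm. The detectable difference at 60 per arm is then 0.516 × 1.603 = 0.83 step, which rounds to 1. This fits nearly everything, and it stands as a possible explanation. What it leaves over is the expectation of at least 2 steps: a difference of 1.70 is below 2, so the text would still need correcting.

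On (b), the reply is that the SAP claims only a detectable size, that the size is right, and that this is a pilot (SAP sections 1 and Future Directions) in a setting where little is known. All of that stands. Having no prior estimate of the spread difference is understandable. The remaining objection is to using 1.2 as the yardstick for the Cluster-versus-Central test.

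Three stronger readings are tempting, and the documents do not support them:
- *The steps comparison is underpowered, or its power cannot be assessed.* The mismatch errs on the safe side, and both power statements hold at either SD.
- *The SAP predicts a 0.6 SD gap between arms.* It says only that the trial could detect one.
- *The number exposed per shift is contradictory.* The power paragraph says at least 10, a lower bound, and elsewhere "although we are targeting only two patients per shift, all the patients on that shift are considered exposed to the COACH education". Planning on a lower bound is compatible with analysing everyone.

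**Conclusion.** Both parts hold, at modest size.

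(a) The printed data give 1.25, not 1.06, and the stated 80% power for 2 steps at 15 per arm is about 91% with the printed SDs. This is a minor, conservative inconsistency. No sample size changes. The documents do not show which figure is wrong.

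(b) The detectable 0.6 SD is correct, but the benchmark is misapplied: 1.2 is COACH's own effect and could inform only the pre-post or taught-versus-untaught assessments. For the between-arm comparison the SAP gives no expected difference, so the claim of power for half of 1.2 does not show that the comparison is adequately powered for a plausible gap. It does not show the reverse either; the 0.2 to 0.5 SD range above is an assumption.

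All power figures assume independent patients although assignment is by shift, and none allows for the 5% drop-out given under Retention/Attrition for Aim 3.

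**What to change.** 1. Check the source data from the earlier network study. Correct whichever of the means, SDs, effect size or its label is wrong, and restate the effect size and the 2-step and 1-step power from the corrected values.
2. Remove 1.2 as the basis for the Cluster-versus-Central knowledge power. State only the between-arm difference detectable with 80% power for the number to be analysed (0.60 SD at 45 per arm, 0.52 SD at 60 per arm, before drop-out), and say that the pilot has no prior estimate of the between-arm difference in spread.
3. Reconcile whether knowledge is primary or secondary (SAP, Analytic plan AIM3), and whether one or two patients per shift receive COACH (Protocol 7.d.iv against SAP Recruitment Goals and Exposure for Aim 3).

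The cost is SAP wording, plus the protocol if the number taught is reconciled there. Recruitment is unaffected. The downside is a less favourable knowledge power claim.
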